4.1. Targeted primary end point and secondary end points (effectiveness and safety parameters)

Main objective is the effect of TMS on psychomotor retardation (PR) in patients with major depressive disorder or schizophrenia. Primary outcome marker will be the change in psychomotor performance as assessed by Salpêtrière Retardation Rating Scales (SRRS). Clinical response will be defined as a 30% reduction of the SRRS baseline scores.

Secondary targets will be the effect of TMS on other motor parameters and on specific symptoms e.g. depressive or negative symptoms.

Efficacy parameters: TMS parameters may be of critical role determining the effect of the applied TMS on motor symptoms.

Safety parameters: As specific safety factors in relation to TMS, patients with 1. past history of epilepsy, or 2. other increased neuronal activity in Electroencephalography (EEG), 3. MRI contraindications and 4. substance misuse will be excluded. EEG recordings will be held for all patients before the beginning of TMS. Patients will be screened every 5 sessions with SRRS and actigraphy. In case of moderate deterioration of motor performance (30% change of initial ratings of SRRS or/and actigraphy) or adverse reactions during the TMS protocol, patients will be excluded from further participation in the study. .

4.2. Specification of the parameter that is of primary interest and other parameters that will be assessed as additional, secondary end points.

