7.1. Safety parameters: measuring methods and times

Specific safety parameters for TMS include: past history of epilepsy, pregnancy, other increased neuronal activity in Electroencephalography (EEG), MRI contraindications and substance misuse other than nicotine. Female patients will take a urine pregnancy test before the beginning of the TMS sessions and they will be required to use contraceptive methods during the **study** in order to enroll in the study. In case of a suspicion of a pregnancy during the **study** despite the use of contraceptives a urine test will be taken. These parameters will be observed and are explicit exclusion criteria. EEGs of all patients will be recorded before the beginning of TMS. Patients displaying abnormal EEG findings will be excluded. The rest of above mentioned parameters will be as well observed and are explicit exclusion criteria. After every 5 sessions, assessments of gross motor behaviour (SRRS,

actigraphy) will be repeated. In case of moderate deterioration of motor performance (30% change of initial ratings) patients will be excluded from the **study**.

7.2. Guarantee of follow-up examination of patients in case of adverse reactions.

The study will be carried out according to the protocol. In case of serious adverse events, which may be connected to the TMS **stimulation** or any relevant assessments (Art.42, KlinV), the Ethics Committee will be as soon as possible informed by the sponsor. Serious adverse events may include seizures or exacerbation of psychiatric symptoms. In such cases the TMS sessions will be immediately stopped and the patient will be excluded from the study. A MRI examination will be held and any necessary additional medical consultations will be arranged.

8. Statistics

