8.1. Definition of the primary end point and secondary end points

Primary outcome of the study will be clinical response as defined by >30% improvement from the baseline score of the Salpêtrière Retardation Rating Scales (SRRS). Moreover, gross motor behavior (actigraphy), fine motor function (finger tapping test), and hand gesture performance (TULIA) will be assessed at baseline and after the last TMS. Furthermore, we will investigate the efficacy of TMS on disorder specific symptoms; in patients with major depressive disorder, HAMD, MADRS and BDI, in patients with schizophrenia PANSS, SANS, CAINS and the Bush Francis Catatonia Rating Scales will be carried out before and after TMS. Statistical analysis will comprise ANOVAs of motor variables and stimulation mode as between subject variable. Clinical response will be defined as a 30% reduction of the SRRS scores. Frequency of response will be compared between groups using Chi²-Tests.

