8.5. Handling of missing data, dropout cases

Only complete data records with assessments at two time points will be entered in the analyses. In case of dropout we will perform an intention-to treat (ITT) analysis applying the last-observation-carried-forward method (LOCF). In case of revocation of patients (KlinV, Art.9), data will be anonymized.

9. Study-specific safety precautions and responsibilities

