9.1. Safety precautions

The specific risks for TMS include past history of epilepsy, pregnancy, other increased neuronal activity in Electroencephalography (EEG), MRI contraindications and substance misuse other than nicotine. EEGs of all patients will be recorded before the beginning of TMS. Patients displaying abnormal EEG findings will be excluded. Female patients will take a urine pregnancy test before the beginning of the TMS sessions and they will be required to use contraceptive methods during the **study** in order to enroll in the study. In case of a suspicion of a pregnancy during the **study** despite the use of contraceptives a urine test will be taken. The rest of above mentioned parameters will be as well observed and are explicit exclusion criteria.

After every 5 sessions, assessments of gross motor behaviour (SRRS, actigraphy) will be repeated. In case of moderate deterioration of motor performance (30% change of initial ratings) during the **study**, patients will be excluded from the TMS. The investigators are responsible for the observation of the above mentioned criteria and the screening of patients. Patients will have to provide written informed consent, which will include explicit questions referring to the exclusion criteria. The safety criteria will be asked again before the beginning of TMS **sessions** and participants will have to warrant that none of the exclusion criteria is fulfilled.

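### Section 8.5 lets LOCF carry a mid-course SRRS into the responder endpoint, so a patient taken off TMS early can count as a responder to the 3-week course

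*Combined protocol and SAP*

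**What the plan says.** - **Endpoint and test (8.1).** "Primary outcome of the study will be clinical response as defined by >30% improvement from the baseline score" of the SRRS; "Frequency of response will be compared between groups using Chi²-Tests".
- **Missing data (8.5).** There are two rules, one after the other. First: "Only complete data records with assessments at two time points will be entered in the analyses". Then: "In case of dropout we will perform an intention-to treat (ITT) analysis applying the last-observation-carried-forward method (LOCF". The section does not say which rule governs the primary endpoint, or which SRRS value is carried.
- **Ratings during the course.** Section 4.1: "Patients will be screened every 5 sessions with SRRS and actigraphy". Section 9.1: "After every 5 sessions, assessments of gross motor behaviour (SRRS, actigraphy) will be repeated". Sections 7.1, 9.2 and 4.3 (Course of the study) agree. Section 6.1, however, speaks of clinical ratings at only two times, baseline and after the final session.
- **Removal (4.1).** "In case of moderate deterioration of motor performance (30% change of initial ratings of SRRS or/and actigraphy) or adverse reactions during the TMS protocol", the patient takes no further part. Sections 7.2 and 10.2 stop TMS and exclude the patient after a serious adverse event.
- **Exit rating (9.2).** The section headed as the exit examination describes the weekly ratings and an MRI in stated circumstances. It sets no separate exit SRRS.

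No section says whether a removed patient is a responder or a non-responder.

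**The concern.** The primary endpoint is meant to describe response to a 3-week course of 15 sessions. If the last available SRRS is carried forward, a patient who improved early and was then taken off treatment adds a success to that arm. The protocol's stopping rule and its endpoint can then judge the same patient in opposite ways.

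Arms are small and the test is a chi-square on counts, so a few such patients matter. Section 8.3 also repeats the primary analysis at 25%, 50% and 75% of recruitment and may close an arm on the result. At 25% there are 0.25 × 80 / 4 = 5 patients per arm, and one patient is 20 percentage points. With no written rule, the status of removed patients could also be settled after the data have been seen.

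**Working it through.** **1. The plan's own figure.** Section 8.2 sets responder shares of 25/25/40/10% against 25% each.
- w = √[(0² + 0² + 0.15² + 0.15²)/0.25] = √0.18 = 0.424.
- With df = 3, α = 0.05 (critical value 7.81) and N = 79, λ = 79 × 0.18 = 14.22 and power is 0.901.

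The stated 79 reproduces. It contains no allowance for dropout, and the point made here does not change it.

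**2. Each discontinuation path under LOCF.** The baseline SRRS of 30 is illustrative. Response requires (baseline − carried)/baseline > 30%.

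| Path | Carried SRRS | Change | Scored |
|---|---|---|---|
| Adverse reaction after an improved session-5 or session-10 rating | 20 | 33% better | Responder |
| Removed because SRRS worsened by 30% | 39 | 30% worse | Non-responder |
| Removed on actigraphy alone, SRRS improved | 20 | 33% better | Responder |
| Stopped before the first repeat rating | 30 (baseline) | 0% | Non-responder |

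The first and third paths credit a stopped patient. The third needs the two motor measures to disagree, which the wording of 4.1 allows.

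**3. Weight of one patient.** 1/20 = 5 percentage points of an arm's response rate.

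**4. Effect on the primary test.** Pearson chi-square, four arms of 20, no continuity correction. With responder counts x and mean m, X² = Σ(x − m)² × [1/m + 1/(20 − m)]. I assume 29 responders in total, split by the 8.2 shares (2.9, 7.25, 7.25, 11.6) and rounded to 3/7/7/12. This table was chosen to lie near the threshold.
- 3/7/7/12: m = 7.25, Σ(x − m)² = 40.75, X² = 40.75/7.25 + 40.75/12.75 = 8.82, p = 0.032.
- 3/7/7/11 (one patient in the best arm rescored): m = 7, Σ = 32, X² = 32/7 + 32/13 = 7.03, p = 0.071.
- 3/6/6/12 (one in each middle arm rescored): m = 6.75, Σ = 42.75, X² = 9.56, p = 0.023.
- 2/6/6/11 (one in every arm rescored): m = 6.25, Σ = 40.75, X² = 9.48, p = 0.024.

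One patient can decide a borderline result, and rescoring can move p either way.

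**5. How many patients?** The documents give no dropout or interim response rates, so this is a range under assumptions.
- If 10–20% of an arm is stopped (2–4 patients) and 20–40% of those were more than 30% better at the last rating, credited responders are 2 × 0.2 = 0.4 to 4 × 0.4 = 1.6 per arm.
- Section 11.1 puts adverse reactions below 1 in 1000 investigations. Reading an investigation as a session, 20 × 15 = 300 sessions give fewer than 0.3 events per arm. At the same 20–40% share, that is fewer than 0.06–0.12 credited responders per arm.

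**6. Direction.** Suppose 25% of completers respond in every arm, 20% of each active arm stops, and no sham patient stops.
- If 25% of stopped patients were improved, LOCF gives 0.8 × 25% + 0.2 × 25% = 25% in the active arms, equal to sham.
- If 50% were improved, LOCF gives 0.8 × 25% + 0.2 × 50% = 30%.
- Non-responder scoring gives 0.8 × 25% = 20% in both cases.

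The sign of any LOCF distortion therefore depends on rates that the documents do not state.

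**The case against.** **LOCF may not reach the mid-course ratings.** Section 8.5 does not name them, section 6.1 counts only two rating times, and most mentions of the repeat ratings stand under safety. If only baseline can be carried, every dropout is already a non-responder. This stands as a real ambiguity. It is the weaker reading, though: section 4.3 lists the repeat assessments in the course of the study and has rating data prepared for analysis alongside them, and a rule that always returns baseline would not normally be called LOCF. If baseline was meant, the fix only makes that explicit.

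**The complete-records sentence may drop these patients.** It may, but that shows 8.5 is unsettled, not that the scoring is safe.

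**Stops may be rare.** Section 11.1 supports this for adverse reactions. However, the adverse-reaction trigger in 4.1 has no severity threshold, and voluntary withdrawals are carried forward in the same way.

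**Two stronger readings are tempting and should not be drawn.** A reader might infer that any patient removed for motor deterioration can be scored a responder. That fails when SRRS is the trigger, because the carried score is then worse than baseline. A reader might also infer a bias towards active stimulation, since sham uses a placebo coil expected to do little. No stop rates or interim response rates by arm are given, and early stops carried at baseline work the other way.

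**Scoring every stop as non-response changes what is measured.** This also stands: the endpoint then combines improvement with completing the course. That is defensible for a treatment course, but it is a choice and should be written down.

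**Conclusion.** The point holds in limited form. Section 8.5 contains two competing rules. Under the natural reading of LOCF, a patient more than 30% better at session 5 or 10 is a responder even if then removed for an adverse reaction, or on actigraphy alone. Nothing in the documents prevents this. Removal triggered by SRRS is unaffected.

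Each such patient is worth 5 percentage points in an arm of 20 and can decide a borderline chi-square. How many there will be, and which arms they would favour, cannot be derived. The range of 0.4–1.6 per arm rests on assumed stop rates, and the adverse-reaction figure in 11.1 points to far fewer from that cause. This is a cheap improvement that closes an open choice before the data are seen. It does not show that the planned result would be biased.

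**What to change.** In 8.1 and 8.5:

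1. State that the primary chi-square includes all randomised patients in their allocated arms.
2. State that any patient without an SRRS after the last planned session is a non-responder, whether removed under the protocol's stopping rules or withdrawn voluntarily. Say planned, because for a patient who stops early the last session received is a different one.
3. Delete the complete-records sentence for this endpoint, or restrict it to other analyses.
4. Report LOCF, naming the SRRS value carried, and complete cases as sensitivity analyses.
5. Apply the same scoring at the interim looks in 8.3.

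**Cost.** A few sentences, no new data and no change to the 79. Observed response rates fall slightly in arms with dropouts. If dropout is much more common in active arms, this scoring works against them (20% against 25% in the example above), which is why the sensitivity analyses are needed. No stopping or clinical rule changes.

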9.1. Safety precautions

The specific risks for TMS include past history of epilepsy, pregnancy, other increased neuronal activity in Electroencephalography (EEG), MRI contraindications and substance misuse other than nicotine. EEGs of all patients will be recorded before the beginning of TMS. Patients displaying abnormal EEG findings will be excluded. Female patients will take a urine pregnancy test before the beginning of the TMS sessions and they will be required to use contraceptive methods during the **study** in order to enroll in the study. In case of a suspicion of a pregnancy during the **study** despite the use of contraceptives a urine test will be taken. The rest of above mentioned parameters will be as well observed and are explicit exclusion criteria.

After every 5 sessions, assessments of gross motor behaviour (SRRS, actigraphy) will be repeated. In case of moderate deterioration of motor performance (30% change of initial ratings) during the **study**, patients will be excluded from the TMS. The investigators are responsible for the observation of the above mentioned criteria and the screening of patients. Patients will have to provide written informed consent, which will include explicit questions referring to the exclusion criteria. The safety criteria will be asked again before the beginning of TMS **sessions** and participants will have to warrant that none of the exclusion criteria is fulfilled.

9.2. If appropriate: exit examination in case of dropout

At the end of every week of the **TMS stimulation**, assessments of gross motor behaviour (SRRS, actigraphy) will be repeated. In case of moderate deterioration of motor performance (30% change of initial ratings), patients will be excluded from the **study**. In case of seizures or persisting headaches a Magnetic Resonance Imaging Examination will be held for diagnostic purposes.

10. Duties of the investigator

10.1. Confirmation that the conduct of the study will be in accordance with the GCP protocol, the current legal regulations and rights.

Hereby investigators confirm that they have knowledge of the GCP protocol, according to which the study will be carried out. All current legal regulations and rights will be additionally taken into account.

10.2. Adverse reactions, protocol changes, other changes, progress report and final report

Serious adverse events (SAE) may include seizures or exacerbation of psychiatric symptoms, which may be connected to the TMS or any relevant assessments (Art.42, KlinV). In such cases the TMS sessions will be immediately stopped and the patient will be excluded from the study. Hereby the investigators guarantee that in case of any adverse events, as well as protocol changes or other changes, the Ethics Committee will receive a progress report and final report. Additionally, investigators confirm the knowledge of the AKEK safety reporting procedures (Arbeitsgemeinschaft der Schweizerischen Forschungs- Ethikkomissionen für klinische Versuche).

10.3. Statement of arrangements to cover damages

An insurance policy will be taken out and insurance form according to the requirements of the “schweizerische Ethikkomission” (“Versicherungszertifikat zu Handen der schweizerischen Ethikkomissionen”) is appended in order to assure that any possible damage will be covered.

11. Ethical considerations

11.1. Potential risks/ benefits balance

Clinical ratings & questionnaires:

The clinical tests and the questionnaires are non-invasive methods, used mainly in route examinations with no reported side effects.

TMS sessions:

TMS is a well known, clinical, diagnostic and therapeutic, non-invasive tool, widely used with seldom reported adverse reactions, as supported by an extensive body of studies and meta-analyses (Padberg & George, 2009). In rare single cases, seizures and mild headaches have been reported, while in very few cases negative effects on cognition, mood and various hormone levels were elicited (Wasserman, 1998; Burt et al., 2002). The TMS-induced seizures were in most cases self-limiting, and did not seem to have permanent sequel. Once again, it is important to point out that the risk of adverse reactions is noticeably low, below 1/1000 investigations (Information Brochure on rTMS, rTMS committee of the International Federation of Clinical Neurophysiology). TMS parameters (intensity, frequency, number of stimulations) of the presented study will be in accordance to international safety guidelines (e.g. Wasserman, 1998).

TMS potential adverse effects will be minimized and the risk/benefit ratio will be supportable by following the TMS safety parameters, as they were above described. Any severe adverse effect will lead to discontinuation of the rTMS **protocol** in the respective patient. TMS exclusion criteria are past history of epilepsy, other increased neuronal activity in Electroencephalography (EEG), MRI contraindications and substance misuse. EEG recordings of all patients will be conducted before the beginning of rTMS **sessions**.

11.2. Benefits for the participants

Patients with motor abnormalities are expected to display an improvement of motor performance after receiving different configurations of TMS. A potential beneficial effect of TMS on the disorder specific symptoms may be also detected. Additional benefit will be the gained knowledge, possibly helpful for future patients with the same problems.

Importance of the trial

Psychomotor retardation appears to be of central significance across a spectrum of mental disorders such as schizophrenia and depression subtypes, in which the planning and the execution of movements is affected, resulting in disturbances in main psychomotor domains (Morrens et al., 2007; Schrijvers et al., 2008). The occurrence of PR is strongly associated with poorer quality of life (Muslimovic et al., 2008) and it may have a restraining effect on common physical activities of patients (Putzhammer et al., 2005; Schrijvers et al., 2008). Our study of the efficacy of different TMS protocols on PR will significantly extend the knowledge on the pathophysiology of PR. Moreover, the study will inform on potential mechanisms for noninvasive therapeutic brain stimulation to target psychomotor retardation.

12. Quality control and quality assurance: description of measures

The study conforms to the declaration of Helsinki. Participants will provide written informed consent and will be informed about the option to drop out of the study at any moment.

12.1. Warranty to access to original data, permission of audits and monitoring by authorities, Ethic Committee and quality control

Direct access to original data and inspection by pertinent authorities and Ethic committee will be provided if required.

12.2. Handling of data and samples, archiving and destruction

The data will be encoded (subjects' initials and date of birth will be used to code their data), digitalised and processed exclusively on the local computer of the principal investigator, while a copy of them will be kept on server of the Department of Psychiatric Neurophysiology, University Hospital of Psychiatry in Bern, following the strict security rules of the Department. Only the principal investigator will be aware of the decoded data, while the other investigators will use the encoded data. The encryption key as well as the list of the participants will be kept by the main investigator. The encryption code and the list guarantee the traceability of the patients' data (KlinV, Art.18). In case of revocation (KlinV, Art.9), data will be anonymized. Paper records will be archived in the archive of the University Hospital of Psychiatry in Bern for 10 years and they will be destructed according to the security rules of the archive. Digital data will be as well preserved for 10 years and afterwards will be deleted. In the meantime they may be used in upcoming studies. No genetic examinations/transfers of samples are planned.

